9.1.1 Schedule of Events

Table 1. Study Activities- Clinic Visits (Day 1/Baseline Through 6 months)

Activity	Baseline (Day 1) ^a	Any time point between 3-6 months
Inclusion/Exclusion Criteria	X	
Informed Consent	X	
Demographics†		
Medical History*	X	
TB History Assessment ^b	X	
Concomitant Medications, Including Changes to	X	X
CRP (if available) ^c	X	X
Physician’s Assessment of Disease Activity: Active joint count, or CDAI, or PASI	X	X
Adverse Events ^d	X	X

† Once the physician has determined that the patient is eligible for inclusion, and the patient has agreed to be included in the observational study, the patient's demographic data (including year of birth, gender, ethnicity) will be recorded on the CRFs at the Baseline visit

[figure not shown]
*The physician will determine the patient's current health status and obtain a complete medical history including history of tobacco, date of diagnosis, disease activity, concomitant medications and TB exposure/risk factors at the Baseline visit.

Table 2. Study Activities- Patient Activities (Day 1/Baseline Through 6 months)

Activity	Baseline (Day 1) ^a	2 months	4 months	6 months
WHODAS 2.0 12-item version, self-administered	X	X	X	X
Disease-specific patient reported outcomes: HAQ-DI or SIBDQ or DLQI	X	X	X	X
Kessler Psychological Distress Scale (K10)	X	X	X	X
Work Productivity and Activity Impairment Questionnaire	X	X	X	X
Flourishing Scale	X	X	X	X
Subject Vitality Scale	X	X	X	X

- a. The Baseline visit date will serve as the reference for all subsequent visits. A \pm 7 day window is permitted around scheduled study visits, however at Baseline patient questionnaires must be completed prior to the first dose of adalimumab.
- b. An assessment of TB exposure/risk factors for active and latent TB (per local requirements and according to the approved adalimumab NZ Datasheet) must have been completed prior to the first dose of adalimumab with documented history of results
- c. CRP will only be collected if procedure is performed as part of the usual standard of care
- d. Collection of adverse events begins the day the Subject signs the informed consent

Figure of study design:

*Disease-specific measure of response to treatment:

- Active joint count, or CDAI, or PASI

**PRO questionnaires (all self-administered):

- WHODAS 2.0 12-item version
- WPAI:GH V2.0
- K10
- Flourishing Scale
- Subject Vitality Scale
- Disease-specific outcomes: HAQ-DI or SIBDQ or DLQI

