9.1.4 Adalimumab dosing

The participating Physician will provide the patient with a prescription for adalimumab, along with instructions for appropriate use. The date of first dose of adalimumab will be recorded in the CRF and should closely align with the Baseline visit, but not before completion of the PRO questionnaires.

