It is the Investigator's responsibility to ensure that all inclusion/exclusion criteria are met. Subject selection may be completed by use of a relevant record (e.g. checklist of inclusion/exclusion criteria). Site personnel should thoroughly assess the eligibility criteria and evidence of this should be stored with the source documentation at site.

Where there is any deviation from the inclusion/exclusion criteria, the patient should be excluded from the study.

9.2.1 Inclusion Criteria:

1. Male and female
2. 18 to 75 years of age, inclusive.
3. Patients with a diagnosis of rheumatoid arthritis, Crohn's disease or psoriasis who have made a decision with their physician to commence treatment with adalimumab in accordance with routine medical practice and with the approved adalimumab New Zealand datasheet.
4. Patients who have been evaluated for tuberculosis risk factors/exposure for active/latent tuberculosis infection (per local requirements and according to the approved adalimumab New Zealand Datasheet).
5. Subject has voluntarily signed and dated an informed consent form, prior to any study-specific procedures.

9.2.2 Exclusion Criteria:

1. Previous treatment with adalimumab
2. Previous treatment with any biologic
3. Severe infection including sepsis, active tuberculosis or opportunistic infection.
4. Moderate to severe heart failure (New York Heart Association Class II/III)
5. Concurrent administration with anakinra
6. Hypersensitivity to adalimumab or its excipients
7. Any condition that in the opinion of the investigator would compromise the subject's well-being or ability to perform the study requirements.

The duration of the study will be up to 6 months. Study visits are Screening/Baseline (Day 1) and 2 months, 4 months and 6 months.

There is a \pm seven (7) day window for all study visits. An effort will be made to bring subjects back to their original scheduled visit (calculated from Baseline) if they are out of the visit window for more than one visit.

For subjects who discontinue from the study prematurely a phone call will be made 30 days after the last dose of adalimumab is administered to obtain follow-up information on any ongoing or new adverse events.

9.2.3 Discontinuation of Individual Subjects:

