Each subject has the right to withdraw from the study at any time. In addition, the investigator may discontinue a subject from the study at any time if the investigator considers it necessary for any reason, including the occurrence of an adverse event. If the reason for treatment discontinuation is due to a serious adverse event, it should be reported to AbbVie within 24 hours of physician's awareness.

In the event that a subject withdraws or is discontinued from the study, the primary reason for discontinuation and any other reason(s) for the discontinuation from the study will be recorded. Following discontinuation of the study drug, the patient will be treated in accordance with the Investigator's best clinical judgment.

For subjects who discontinue from the study prematurely a phone call will be made 30 days after the last dose of adalimumab is administered to obtain follow-up information on any ongoing or new adverse events.

Subjects will be withdrawn from the study immediately if any of the following occur:

- The investigator believes it is in the best interest of the subject.
- The subject or subject's guardian requests withdrawal from the study.
- A selection criteria violation was noted after the subject started study drug.

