9.8 Data Analysis

9.8.1 Definitions

9.8.1.1 Participant Population

All participants who are recruited into the study and start study medication will be used for analysis. A full analysis set will be used for the analysis of the efficacy outcomes with all available data used for the analyses of each outcome at the relevant time points. Efficacy measures are not assessed after a participant discontinues adalimumab. The exception to this will be the analysis of proportion of patients at 6 months who remain on adalimumab, having satisfied the requirements for application for renewal of subsidy by Special Authority. Any participants for whom this assessment is not available will be assumed to have not met these requirements. The primary population for the evaluation of study safety objectives will be the safety population, defined as all participants enrolled into the trial who started study medication. Safety outcomes will only be considered while the patient is on adalimumab. A standard consort diagram describing participant flow (including loss to follow-up and discontinuations for any reason) through the study will be generated.

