9.8.1.2 Observational Period

The observational period will be from participant enrolment to 6 months or until any participant stops study medication or withdraws from the study.

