9.8.6 Safety Analyses

Adverse events occurring while participants are on adalimumab will be coded using CTCAE classification individually listed by indication groups. The incidences and percentages of individuals experiencing AEs and SAEs within each indication will be summarized by System Organ Class (SOC) with further summaries by severity and relatedness (causality) categories. Adverse events leading to discontinuation and concomitant medications will also be listed and summarised.

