11.4 Serious Adverse Event Collection Period

Serious adverse events will be reported to AbbVie from the time the physician obtains the patient's authorization to use and disclose information (or the patient's informed consent) until 30 days or 5 half-lives following the intake of the last dose of physician-prescribed treatment.

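### Safety outputs are limited to time on adalimumab, so on the plain reading events collected after treatment stops enter no planned table or listing

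*Combined protocol and SAP*

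**What the plan says.** **Analysis.** Section 9.8.1.1 defines the safety population as everyone enrolled who started medication, and then limits the time that counts: "Safety outcomes will only be considered while the patient is on adalimumab". Section 9.8.6 repeats the limit where events are processed: "Adverse events occurring while participants are on adalimumab will be coded". Section 9.8.1.2 sets an observational period from enrolment to 6 months or "until any participant stops study medication or withdraws from the study".

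**Collection.** The collection rules reach further at both ends.

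- At the start (section 9.1.1, footnote d): "Collection of adverse events begins the day the Subject signs the informed consent". The first dose follows the baseline questionnaires. Section 9.1.4 says: "The date of first dose of adalimumab will be recorded in the CRF and should closely align with the Baseline visit".
- At the end, for AEs (section 9.2.2, in the text after the exclusion criteria, and again in 9.2.3): "For subjects who discontinue from the study prematurely a phone call will be made 30 days after the last dose of adalimumab is administered". Its purpose is "to obtain follow-up information on any ongoing or new adverse events".
- At the end, for SAEs (section 11.4): reporting continues "until 30 days or 5 half-lives following the intake of the last dose of physician-prescribed treatment".

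**The concern.** The follow-up call asks about new events, so onset after the last dose is sought on purpose. The safety analysis then admits only time on drug. If the plan is followed literally, an event reported at that call, or an SAE reported under 11.4 after treatment has ended, has no place in the coded listings or in the System Organ Class tables. The study report could be silent on it.

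Stopping treatment is a foreseeable part of this design. Section 9.1 makes continuation depend on meeting disease-specific response criteria between 3 and 6 months, so some patients are expected to stop within the study.

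The end of the window is also left open. If one programmer takes treatment to end on the last-dose date and another adds a tail, the same event can fall on different sides of the cut-off.

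**Working it through.** The plan states no figure on this point, so there is none to reproduce. The check sets the windows side by side.

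**1. Windows compared**

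| Period | Collected? | In a planned AE/SAE output? |
|---|---|---|
| Consent to first dose | Yes (9.1.1, footnote d) | No, on the plain reading of 9.8.1.1 and 9.8.6 |
| On adalimumab | Yes | Yes (9.8.6) |
| After last dose, AEs | Yes, by the 30-day call, in premature study discontinuers (9.2.2, 9.2.3) | No, on the plain reading |
| After last dose, SAEs | Yes (11.4) | No, on the plain reading |

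The incidence tables in 9.8.6 carry no window of their own, so the general rule in 9.8.1.1 governs them.

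**2. Does another section bring these events back?**

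- Section 9.8.1.2 does not mention safety. It starts at enrolment, which is earlier than first dose, but it too ends when medication stops.
- Section 9.8.2 promises listings of safety data at relevant time-points. It names neither period and does not clearly override the explicit limit in 9.8.1.1.
- The safety population settles who is counted, not over what time.
- The 24-hour SAE reporting in 11.5 is notification to the sponsor, not a planned analysis.

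None of the four supplies an output for events that begin after treatment stops.

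**3. Size**

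The documents give no stopping rate, event rate or stopping times, so a count of affected events cannot be calculated. What can be shown is the follow-up of one patient who does receive the call. If that patient's last dose falls on day d (assumed) after the first, the share of the first-dose-to-call period lying after the last dose is 30 / (d + 30):

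- d = 30: 30/60 = 50%
- d = 61: 30/91 = 33%
- d = 91: 30/121 = 25%
- d = 122: 30/152 = 20%
- d = 152: 30/182 = 16%

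These are shares of one such patient's time. They are not event counts and do not describe the cohort.

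**4. The two limits in 11.4**

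The two alternatives coincide only if the half-life is 30 / 5 = 6 days. The documents give no half-life and do not say which alternative applies, so the SAE limit cannot be matched to the 30-day call from the text alone.

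**5. Before the first dose**

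Section 9.1.4 expects the first dose close to Baseline but sets no maximum in days. The gap is probably short, and these events precede exposure.

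**The case against.** The strongest reply is that this is a stated and consistent choice. Sections 9.8.1.1 and 9.8.6 agree with each other, 9.8.1.2 also ends when medication stops, and collecting more widely than one analyses is not a contradiction. Section 11.4 sets a notification duty and the call is follow-up; neither promises a table. The study is non-interventional, and section 8 and the endpoint list in 9.1 name no safety endpoint. This stands as far as it goes: an on-treatment analysis is a legitimate main analysis. It does not explain why events sought on purpose should have no output at all.

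A reader might also infer more than the text supports.

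- **That the on-treatment period is wholly undefined.** Sections 9.8.1.1 and 9.8.1.2 refer to starting and stopping medication, which gives a natural start and end. The open question is whether time after the last dose is included.
- **That events leading to discontinuation are lost.** Those that begin on drug are listed and summarised under 9.8.6.
- **That a definite share of safety follow-up is discarded.** Suppose 10% or 40% of 190 patients stop at 120 days, all receive the call, and the rest have 180 days. This gives 19 × 30 / (171 × 180 + 19 × 150) = 570/33,630 = 1.7%, or 76 × 30 / (114 × 180 + 76 × 150) = 2,280/31,920 = 7.1%. The documents do not support such a range. The rates and stop time are assumed. The call goes to premature study discontinuers, which need not mean every patient who stops the drug; the Abstract's comparison with patients not continuing adalimumab suggests that some may stay in the study. Table 1 schedules AE recording only at Baseline and once between 3 and 6 months, so 180 days of AE follow-up is also an assumption.
- **That the last-dose date is not captured.** Section 9.1.4 names only the first-dose date, but the call and 11.4 both need the last. The CRF is not in the documents, so this cannot be judged.

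**Conclusion.** The concern holds for events with onset after treatment stops. On the plain reading of 9.8.1.1 and 9.8.6, AEs and SAEs that the protocol deliberately collects after the last dose enter no planned table or listing. Events between consent and first dose are in the same position, with little consequence.

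The conclusion rests on reading time on adalimumab as ending when treatment stops. If the sponsor intends a tail, the gap narrows, but the plan does not say so. The number of events affected cannot be derived. The primary endpoint is unaffected and SAEs still reach the sponsor, so what is at stake is the completeness of the reported safety results, chiefly non-serious events after stopping and the display of post-treatment SAEs. This is a cheap improvement that should be made; it does not undermine the study.

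**What to change.** - In 9.8.1.1 and 9.8.6, tie the on-treatment window to first- and last-dose dates, and state whether it includes a tail. The sponsor decides this.
- Keep the on-treatment tables as the main safety analysis.
- Add one separate coded listing and summary, by indication, of all other collected AEs and SAEs in the safety population, each flagged as before first dose or after the window.
- Reconcile the post-dose collection wording in 11.4 with that in 9.2.2 and 9.2.3. No length is proposed here.

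**Cost.** Text edits to these sections, plus one listing and one table. The events are already collected. The drawback is unequal post-dose follow-up: because the AE call goes only to premature study discontinuers, non-serious post-treatment events will mainly describe them. The summary must be labelled accordingly and must not be merged with the on-treatment incidences.

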9.8.1.2 Observational Period

The observational period will be from participant enrolment to 6 months or until any participant stops study medication or withdraws from the study.

9.8.2 Statistical Analyses

The primary analysis of study efficacy measures will be performed using the full analysis set.

Tables showing standard descriptive statistics (including means, standard deviations, standard errors, medians, ranges and frequencies and percentages), graphs, and participant data listings will be used to summarize the baseline demographic and clinical characteristics, and the efficacy and safety data at relevant time-points. Tabular and graphical summaries will represent data separately for each indication group.

9.8.3 Demographic and Baseline Characteristics

Participant demographic and baseline clinical characteristics will be summarized descriptively by indication group. No hypothesis testing will be performed for these summaries.

9.8.4 Primary Efficacy Analyses

The primary efficacy outcome is the change in the total WHODAS 2.0 score at 6 months after the initiation of adalimumab, across all indication groups. This change will be summarised as the mean and 95% confidence interval and will be tested with a general linear model which includes participant, indication and baseline WHODAS 2.0 score as terms in the analysis.

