9.6 Study Size

It is anticipated that the three groups will respond differently to adalimumab treatment over the study period and there is reason to believe that these groups will be different at baseline. Therefore, the sample size will be powered for rheumatoid arthritis and Crohn's disease. Approximately 80 subjects will be enrolled into each of these 2 parallel study groups allowing for detection of within participant effect sizes of approximately 0.40 as statistically significant (2-tailed $\alpha=0.05$) with 90% power. A minimum of 30 subjects with psoriasis will also be enrolled. A minimum number of 190 patients will be enrolled into the study. The maximum number of rheumatoid arthritis and Crohn's disease patients will be N=100 in each arm, respectively.

Psoriasis patients make up a much smaller proportion of the population who currently receive adalimumab therapy in New Zealand. Therefore, a smaller number of patients (N=30) are sought to be enrolled in this study to ensure the trial population is representative of the general patient population. The maximum number of psoriasis patients will be N=50.

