9.8.5 Secondary Efficacy Analyses

The following secondary endpoints will be analysed and summarised using general linear models and paired t-tests. The analyses summarising the changes across all indications will include participant, baseline levels and indication as terms in the analyses. Those analyses analysing changes within indications will use paired t-tests. Mean changes will be summarised with 95% confidence intervals derived from these analyses.

- Change in total WHODAS score 2 and 4 months after the initiation of adalimumab across all indications
- Change in total WHODAS score 6 months after the initiation of adalimumab in each indication
- Changes in WPAI:GI, K10, Flourishing Scale, and Subject Vitality Scale scores at 2, 4 and 6 months after the initiation of adalimumab, across all indications

- Change in disease-specific scores (HAQ-DI, SIBDQ, DLQI) at 2, 4 and 6 months after the initiation of adalimumab, in each indication

The proportion of patients at 6 months who remain on adalimumab, having satisfied the requirements for application for renewal of subsidy by special authority as defined below for each indication will be summarised for all indications combined and separately. These proportions will be summarised with exact 95% confidence intervals.

- **Rheumatoid arthritis:** $\geq 50\%$ decrease in active joint count from baseline AND a clinically significant response to treatment in the opinion of the physician
- **Crohn's disease:** CDAI score reduction by 100 points or CDAI score ≤ 150
- **Psoriasis:** PASI score reduction of $\geq 75\%$; or in the case of a patient had severe chronic plaque psoriasis of the face, or palm of a hand or sole of a foot at the start of treatment, the patient has a reduction in the PASI symptom subscores for all 3 of erythema, thickness and scaling, to slight or better, OR $\geq 75\%$ reduction in affected skin area.

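### Where baseline acts as a covariate in the single-arm model for mean change (9.8.4, 9.8.5), the standard error is too small; with participant as a fixed effect the model is either the paired t-test or cannot be fitted

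*Combined protocol and SAP*

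**What the plan says.** For the primary outcome, Section 9.8.4 states that the across-indication change in total WHODAS 2.0 at 6 months "will be tested with a general linear model which includes participant, indication and baseline WHODAS 2.0 score as terms in the analysis". It also promises a mean and 95% confidence interval, but ties the model only to the test.

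Section 9.8.5 extends the model to the secondary outcomes: "The analyses summarising the changes across all indications will include participant, baseline levels and indication as terms in the analyses". Here the source of the intervals is explicit: "Mean changes will be summarised with 95% confidence intervals derived from these analyses". Changes within a single indication are analysed by paired t-test.

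The Data Analysis part of Section 4.0 names a paired t-test for the primary endpoint, in patients continuing on adalimumab, with no covariates.

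The plan does not give the data layout (one change per person, or separate baseline and follow-up rows), whether participant is fixed or random, the baseline value at which the mean is evaluated, or the contrast tested.

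**The concern.** Adjusting for baseline is sound when two treatment groups are compared. Here every subject receives adalimumab and the parallel groups are diseases, so baseline adjusts no treatment contrast. The mean change is the month-6 mean minus the baseline mean, and both are subject to sampling error. A covariate model conditions on the observed baselines. At the sample mean baseline and the observed mix of indications it returns the raw mean change, but with a standard error that treats the baseline mean as known.

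At stake are the stated two-sided 5% level of the primary test and the coverage of the across-indication secondary intervals. The paired t-tests within indications carry the full error, so pooled and by-disease intervals would not be on the same footing.

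**Working it through.** **Inputs.** Section 9.6 gives two-sided alpha 0.05, 90% power, a within-participant effect of about 0.40, and 80 + 80 + 30 = 190 subjects. Model terms are from 9.8.4 and 9.8.5. The documents give no SDs and no correlation r between baseline and month 6, so these are assumed and shown as a range.

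**The plan's own figure.** Section 9.6 says "Approximately 80 subjects will be enrolled into each of these 2 parallel study groups". The paired formula gives n = ((1.960 + 1.282)/0.40)² = 66, or 68 with the exact t distribution. At n = 80 the power is 94.2%. An allowance of 15% would give 68/0.85 = 80, but no dropout rate is stated. The stated size is on the generous side, and nothing below depends on it.

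**What the listed terms can mean.** Simulated rejection with no true change, 80/80/30 subjects, r = 0.5 and equal SDs:

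| Reading | What happens | Rejection |
|---|---|---|
| One change per person, participant fixed | Rank 190 on 190 rows: no residual df | no test exists |
| Baseline and follow-up rows, participant fixed | Rank 191 with or without indication and baseline: both drop out, leaving the paired t-test | 5.1% |
| One change per person, participant omitted | Baseline operates | 9.0% |
| Changes at 2, 4 and 6 months, participant random | Baseline operates; model SE 0.0628 against true 0.0730 | 11.6% |
| Baseline and follow-up rows, participant variance estimated at zero | Baseline operates; SE ratio sqrt((3 + r)/4) = 0.935 | 6.7% |

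The 11.6% rests on only 250 runs (Monte Carlo error sqrt(0.116 × 0.884/250), about 2 points). The other percentages rest on 12,000 runs.

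**Size for change = indication + baseline, equal SDs s.** The model is evaluated at the sample mean baseline.

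- Var(change) = 2s²(1 − r)
- Var(change given baseline) = s²(1 − r²)
- SE ratio = sqrt((1 + r)/2)
- True two-sided alpha = 2(1 − Φ(1.96 × ratio))

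| r (assumed) | SE ratio | True alpha | Coverage of 95% CI | Simulated alpha | Simulated, baseline removed |
|---|---|---|---|---|---|
| 0.3 | 0.806 | 11.4% | 88.6% | 11.3% | 5.1% |
| 0.5 | 0.866 | 9.0% | 91.0% | 9.0% | 5.1% |
| 0.7 | 0.922 | 7.1% | 92.9% | 6.7% | 4.5% |

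**Unequal SDs.** If the month-6 SD is k times the baseline SD, the ratio is sqrt(k²(1 − r²)/(1 + k² − 2rk)). At r = 0.5:

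- k = 0.8: sqrt(0.48/0.84) = 0.756, alpha 13.8%
- k = 1.2: sqrt(1.08/1.24) = 0.933, alpha 6.7%

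If baseline and change are uncorrelated (rk = 1), the ratio is 1 and alpha is 5%.

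**How many intervals.** WHODAS at months 2 and 4 gives 2. WPAI, K10, Flourishing and Vitality at three visits give 4 × 3 = 12. The total is 14 if WPAI counts as one score. Section 9.1 speaks of WPAI scores in the plural, so there may be more.

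**Effect on the primary conclusion.** At r = 0.5 the model test and a paired t-test disagree for a raw |t| between 1.96 × 0.866 = 1.70 and 1.97. With all 190 subjects that is a standardised change of 1.70/√190 = 0.12 to 1.97/√190 = 0.14. At the planned 0.40 the expected t is 0.40 × √190 = 5.5.

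**The case against.** The strongest reply is that the plan does not specify change = indication + baseline. Participant is the first term listed, and a participant term makes sense in a general linear model only with more than one row per person. With baseline and month-6 rows and participant fixed, the time contrast is exactly the paired t-test and its standard error is correct. A reader might infer from the baseline term alone that the primary test is anti-conservative however it is run. The documents do not support that, because they leave the layout and the status of participant open. This part of the reply stands, and the point is conditional for that reason.

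It does not clear the plan. The one valid reading is valid only because the listed baseline and indication terms do nothing, and the other fixed-effect reading yields no test. An analyst who wants baseline to operate must omit participant or make it random, and the standard error is then too small.

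A second reply is that the covariate-model standard error is correct for the mean change conditional on the observed baselines. That is true, but Sections 8.0 and 9.8.4 state the mean change without such a condition.

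A third reply is that the size rests on an assumed correlation and that the planned effect is far from the disputed region. Both are fair. They limit the consequence for the primary test but leave the secondary interval widths wrong.

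**Conclusion.** The point holds in conditional form. Wherever baseline operates as a covariate, the standard error of the across-indication mean change is too small. With equal SDs and r from 0.3 to 0.7, the change-score model has a true two-sided alpha of about 11% to 7%. At r = 0.5, SD ratios of 0.8 and 1.2 give about 14% and 7%. All these figures rest on assumed correlations and SDs, and the shortfall vanishes if baseline and change are uncorrelated.

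Three stronger inferences are not supported:

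- **That the primary confidence interval is too narrow.** Section 9.8.4 does not say where that interval comes from. If it comes from raw changes it is correct, but it could then disagree with the model test.
- **That the primary conclusion is likely to be false.** At the planned effect it is unlikely to change.
- **That the estimate is biased.** At the sample mean baseline and the observed indication mix it equals the raw mean change. Equal indication weights could shift it if baselines differ by disease, but the plan does not state the weights.

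The main consequence is at least 14 secondary intervals with less than nominal coverage, not comparable with the by-indication results. In addition, the primary test is left open between Sections 4.0 and 9.8.4.

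**What to change.** In 9.8.4 and 9.8.5, take the mean change, its interval and its test from a single analysis without baseline as a covariate. Either of these would do:

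- Change = indication, weighted by the observed numbers, or a paired t-test.
- A repeated-measures model with the baseline score as one of the responses, indication by visit, unstructured covariance, and the contrast month 6 minus baseline (months 2 and 4 likewise). This also uses the month 2 and 4 scores of patients still on drug who miss month 6.

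Drop the fixed participant term. Keep baseline as a covariate only where indications or subgroups are compared, as in 9.8.7. State the same primary test in Section 4.0 and in 9.8.4, and say that the primary interval comes from it.

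The cost is a few sentences of analysis text before database lock and no new data. Compared with the baseline-adjusted change model, intervals widen by 1/0.922 to 1/0.806, that is about 8% at r = 0.7 to 24% at r = 0.3.
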